9.7. Safety Analysis

All safety analyses will be conducted based on the safety population for the study.

Literature “book” values and normal ranges from local laboratory results will be utilized for this study.

9.7.1. Extent of Study Treatment Exposure and Compliance

Extent of exposure will be assessed within the safety population for the study.

Dose information will be assessed by the following variables:

- Duration of treatment exposure is defined as: last dose date - first dose date regardless of unplanned intermittent discontinuations
- The cumulative dose is the sum of all doses from Cycle 1 to the last dose
- The actual dose intensity is defined as the cumulative dose divided by the duration of treatment exposure in terms of the number of weeks on study
- The relative dose intensity is defined as the ratio of the actual dose intensity to the planned dose intensity. The planned dose intensity is defined as the planned dose for each cycle divided by planned cycle length in weeks
- Dose reduction and reason for dose reduction
- Dose interruption/delays

The number of subjects treated, number of cycles administered, duration of dosing (weeks), cumulative dose (mg), dose intensity (mg/week), and relative dose intensity (%) will be summarized for fedratinib in the study.

Dose interruption, delays and dose reductions will also be analyzed for study IPs within the study.

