3.2. Study Duration for Subjects

The average treatment period for each subject enrolled in the Study is expected to be approximately 12 months. The Survival Follow-up period will last up to 12 months. The total expected study duration for enrolled subjects, including the Survival Follow-up period, will be approximately 2 years. Actual study duration will be dependent upon actual treatment duration for individual subjects.

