9. STATISTICAL CONSIDERATIONS

9.1. Overview

This is a multicenter, single-arm, open-label efficacy and safety study of fedratinib in subjects previously treated with ruxolitinib and with DIPSS-intermediate or high-risk primary myelofibrosis, post-polycythemia vera myelofibrosis, or post-essential thrombocythemia myelofibrosis.

The sections below provide an overview of the proposed statistical considerations and analyses. The final statistical analysis methods will be documented in detail in the statistical analysis plan (SAP).

General Considerations

Descriptive summary for continuous data will include the number of non-missing observations (n), mean, standard deviation, median, minimum and maximum. In addition, 25% percentile and 75% percentile may be provided if needed.

Categorical data will be summarized using counts (n) and percentages (%). The number of subjects with missing data may be displayed but will not be included in the denominator for the calculation of percentages unless otherwise specified.

Unless otherwise specified, baseline value is defined as the last value or measurement taken prior to the first dose in the study.

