9.2. Study Population Definitions

Enrolled Population: this population includes all subjects enrolled into the study.

Safety population: this population will consist of all subjects who were administered at least one dose of fedratinib.

Efficacy evaluable population: this population includes subjects treated with fedratinib with evaluable spleen volume measurements based on MRI/CT scan at baseline and at least one post baseline response assessment by MRI/CT scan. This population will be used for analyses of spleen volume changes.

MFSAF population: For symptoms response (MFSAF version 4.0), fedratinib treated subjects with a Total Symptom Score (TSS) at baseline (eg, symptom score) > 0 and at least 1 post baseline TSS assessment will be included in the analysis.

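### Duration of exposure omits one day, so dose intensity is slightly inflated and cannot be computed for a subject dosed on a single day

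*Combined protocol and SAP*

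**What the plan says.** Section 9.7.1 builds dose intensity from four definitions.

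- Duration: "Duration of treatment exposure is defined as: last dose date - first dose date regardless of unplanned intermittent discontinuations".
- Cumulative dose: "The cumulative dose is the sum of all doses from Cycle 1 to the last dose".
- Actual dose intensity: "cumulative dose divided by the duration of treatment exposure in terms of the number of weeks on study".
- Planned dose intensity: "The planned dose intensity is defined as the planned dose for each cycle divided by planned cycle length in weeks".

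Relative dose intensity (RDI) is actual over planned. Dose intensity in mg/week and RDI in percent are both listed for summary, in the safety population. Section 9.2 defines that population: "this population will consist of all subjects who were administered at least one dose of fedratinib". One dose is therefore enough to be included.

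Section 9.1 adds: "The final statistical analysis methods will be documented in detail in the statistical analysis plan (SAP"). The document reviewed contains no separate SAP derivation of exposure, no added day anywhere else, and no rule for a duration of zero.

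**The concern.** The numerator and the denominator count days differently. The summed dose includes what was taken on the first and the last dosing day, and the planned rate spreads 28 daily doses over 28 days. The duration is a plain difference of dates and is one day shorter than the span over which those doses were taken.

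This has three consequences:

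- A subject who takes every planned dose gets an RDI above 100%.
- The missing day cancels exactly one missed dose, which blurs the measure in a section that is also about compliance.
- A subject with one dosing day has duration 0 and no dose intensity, so a programmer would have to choose a rule without guidance.

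At stake is the accuracy of two descriptive exposure summaries. Cumulative dose, dose reductions and dose interruptions are reported separately and are unaffected.

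**Working it through.** **Inputs.** The dose is 400 mg once daily, continuously, in 28-day (4-week) cycles (section 7.2). The definitions are those of section 9.7.1. Section 3.2 gives the expected exposure: "The average treatment period for each subject enrolled in the Study is expected to be approximately 12 months". The plan states no dose-intensity figure, so there is none to reproduce.

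**Planned rate.** 400 × 28 / 4 = 2,800 mg/week.

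**General factor.** Let D be the number of calendar days from first to last dose, both included, and C the cumulative dose.

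- As written: intensity = C / ((D−1)/7).
- With both end days counted: intensity = C / (D/7).
- Ratio of the two: D/(D−1), whatever doses were missed or reduced in between.

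**Every dose taken at 400 mg.** C = 400 × D, so RDI as written = [400 × D / ((D−1)/7)] / 2,800 = D/(D−1). The inclusive count gives 100% in every row.

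| D (days) | Intensity as written (mg/week) | RDI as written |
|---|---|---|
| 1 | undefined (division by 0) | undefined |
| 2 | 5,600 | 200% |
| 7 | 3,266.7 | 116.7% |
| 14 | 3,015.4 | 107.7% |
| 28 | 2,903.7 | 103.7% |
| 168 (6 cycles) | 2,816.8 | 100.6% |
| 364 (13 cycles, about 12 months) | 2,807.7 | 100.28% |

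**Missed doses within the span.** With N doses of 400 mg taken, RDI as written is N/(D−1) and the inclusive value is N/D.

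- 28 days, 1 missed: 27/27 = 100.0% as written; 27/28 = 96.4% inclusive.
- 28 days, 2 missed: 26/27 = 96.3% as written; 26/28 = 92.9% inclusive.
- 28 days, 7 missed: 21/27 = 77.8% as written; 21/28 = 75.0% inclusive.
- 168 days, 28 missed: 140/167 = 83.8% as written; 140/168 = 83.3% inclusive.

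**Effect on the summary table (illustration).** The documents give no number of early stoppers, so this part rests on assumptions: 110 subjects, all fully compliant, of whom k stop early and the rest have 336 days (336/335 = 100.30%). Then mean RDI = [k × early RDI + (110 − k) × 100.30] / 110.

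- Stop at day 7 (116.67%): 100.3% for k = 0, 100.5% for k = 1, 101.0% for k = 5, 101.9% for k = 11.
- Stop at day 2 (200%): 101.2% for k = 1, 104.8% for k = 5.

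The median stays at 100.3% throughout. With at least one early stopper, the maximum is 116.7% or 200% respectively. The correct value of each of these statistics is 100%.

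**The case against.** The strongest reply is that section 9 is an overview and day-count conventions belong in the SAP, where the formula may already include the extra day. That limits what can be said about the final computation. It does not make the protocol wording right: the formula is explicit, and a SAP that follows it inherits the error.

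A second reply is that the closing words of the actual-intensity definition, about weeks on study, might signal a different denominator. The sentence divides by the duration of treatment exposure, which the same section has just defined, so the phrase reads most naturally as the unit. The figures here depend on that reading. If another denominator was meant, the section needs clarifying anyway.

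Third, the effect is very small at the expected exposure, and the large percentages need subjects who stop within days, for which the documents give no count. The full-compliance scenario is also artificial, since Table 4 provides for holds and reductions. This stands, and it is why the point ranks as minor.

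Fourth, a one-day subject would probably be treated as missing, since section 9.1 bases continuous summaries on non-missing observations; duration and cumulative dose could still be reported. That is plausible, but section 9.7.1 does not say so, and with the inclusive count the question does not arise.

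**Conclusion.** The concern holds, as a minor point. As written, duration is one day short of the inclusive dosing span. Dose intensity and RDI are inflated by D/(D−1) whenever there are at least two dosing dates, and are undefined when there is one.

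Near the expected 12 months the inflation is about 0.3%, and at 6 cycles 0.6%. It becomes visible only for short exposure (3.7% at 28 days, 16.7% at 7 days), so the mean and maximum can move while the median barely does. How far they move depends on how many subjects stop early, which the documents do not give.

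The conclusion is firm for the protocol text, on the reading that the duration already defined is the denominator. It does not extend to what a SAP not seen here may compute. No efficacy analysis, sample-size calculation or error rate depends on it.

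**What to change.** In section 9.7.1, define duration of exposure as (last dose date − first dose date + 1) days, divided by 7 for weeks, and name it as the denominator of actual, and hence relative, dose intensity. Use the same day count in the SAP.

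Full compliance then gives 2,800 mg/week and 100% for every duration, including one day (400 mg over 1/7 week). The change removes the upward bias and the zero denominator and does nothing more.

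The cost is one line of wording and a check of the SAP derivation. Data collection, sample size and endpoints are unaffected.

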9.7.2. Adverse Events

The endpoints of this study are type, frequency, seriousness and severity of AEs, and relationship of AEs to study treatment. The safety population, which includes all enrolled subjects who received at least 1 dose of fedratinib, will be the analysis population for all safety analyses.

Adverse events will be analyzed in terms of TEAEs that are defined to be any event that begins or worsens in grade after the start of fedratinib through 30 days after the last dose. AEs will be summarized by severity/grade based on the NCI CTCAE. If a subject experiences the same AE multiple times during the treatment, the event will be counted only once by the worst grade / greatest severity.

Treatment-emergent adverse events, Grade 3 or higher TEAEs, serious AEs, TEAEs leading to dose reduction, and dose interruption, TEAEs leading to treatment discontinuation, and TEAEs with an outcome of death will be summarized by Medical Dictionary for Regulatory Activities (MedDRA) system organ class and preferred terms. Adverse events of special interest of fedratinib identified in previous trials in a similar population will be summarized in the same manner. If data warranted, additional analyses on fedratinib safety profile may be performed (eg, incidence of nausea, vomiting and diarrhea in relationship to prophylaxis and treatment, etc.) and will be specified in the statistical analysis plan.

9.7.3. Assessment of Risk Mitigation Strategy for Gastrointestinal Adverse Events and Potential Encephalopathy including Wernicke's

Assessment of risk mitigation strategy will include an analysis of incidence of subjects with a CTCAE Grade ≥ 3 of nausea, diarrhea, or vomiting, or occurrence of encephalopathy including Wernicke's (confirmed by brain MRI or autopsy). Analysis of thiamine levels will be at screening, on Day 1 of the first 3 cycles, every third cycle and at the EOT during the study.

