7.4.3. Thiamine Supplementation, Monitoring, and Correction

All subjects receiving study medication will receive thiamine supplementation. Start oral thiamine supplementation at a minimum daily dose of 100 mg (or equivalent) at Cycle 1 Day 1. Continue supplementation throughout the Treatment Period until study medication is discontinued, and through the 30-Day Follow-up visits.

Thiamine levels (for whole blood) will be monitored in all subjects.

- Thiamine levels are assessed at screening and need to be corrected and retested before starting fedratinib treatment (see inclusion criteria)

- While on treatment with study medication, thiamine levels are assessed in a fasting state at start of Cycles 1, 2, 3 and every third cycle thereafter, at the End of Treatment Visit and as clinically indicated
- In case of documented thiamine deficiency and a subject is receiving thiamine supplementation, while on study:
 - Thiamine levels should be assessed in a fasting state and thiamine supplementation should be given after the blood draw
 - If the subject develops signs or symptoms suggestive of encephalopathy including Wernicke's, please follow instruction in Section [7.4.2](#)
 - For thiamine levels below normal range but > 30 nM/L without signs or symptoms of WE while receiving thiamine supplementation:
 - The site should contact the Medical Monitor regarding the low thiamine level as soon as possible
 - Report the event as an Adverse Event of Special Interest (AESI) to the Sponsor.
 - Consider increasing the dose of oral thiamine supplementation to twice the daily dose (if the subject is taking 100 mg, increase to 200 mg)
 - Monitor thiamine level closely (monthly at least) and adjust dose as needed
 - For thiamine level < 30 nM/L **without signs or symptoms** of WE while receiving thiamine supplementation:
 - The site should contact the Medical Monitor regarding the low thiamine level as soon as possible
 - Report the event as an Adverse Event of Special Interest (AESI) to the Sponsor.
 - Study medication must be held until thiamine levels are restored to normal range.
 - Immediate treatment with IV thiamine (stop oral thiamine), at therapeutic dosages eg, 500 mg IV infused over 30 minutes 3 times daily for 2 to 3 days or alternatively IM in equivalent doses according to local standard of care
 - This will be followed by 250 mg to 500 mg IV thiamine infused once a day for 3 to 5 days or alternatively IM in equivalent doses according to local standard of care

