9.7.4. Laboratory Results

Analysis of laboratory data will be descriptive and conducted on the safety population. Summary of laboratory data (including thiamine levels) and change from baseline will also be performed by subject and by cycle. For each of the parameters, a baseline value is defined as the last value or measurement taken up to the first dose of fedratinib.

Hematological toxicities will be assessed from laboratory parameters. Worst NCI CTCAE grades of leukopenia, neutropenia, thrombocytopenia, and anemia will be calculated according to the NCI common terminology criteria.

Qualitative and quantitative results will be summarized for hematological toxicities. Qualitative data (worst NCI CTCAE grade) will be summarized by cycle and by subject.

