1. JUSTIFICATION FOR AMENDMENT

As of 12 Nov 2020, BMS – Celgene has made the decision to not implement the sub-study due to the coronavirus disease 2019 (COVID-19) pandemic's impact on the sub-study start-up activities.

In the ongoing clinical program, BMS has observed events of low thiamine and one case of Wernicke's encephalopathy which was discussed with the Scientific Steering Committee. The Steering Committee made the recommendation to implement prophylactic thiamine supplementation for all study subjects.

This amendment will therefore include updated language to reflect the mandatory thiamine supplementation and updated guidelines for thiamine deficiency as well as the removal of all sub-study language.

The protocol has been revised to remove this optional sub-study throughout the protocol from the Cover page through Sections 11, including figures and tables. The subsections added in Protocol Amendment 1; which separated sections referred to as the “Main Study” and “Sub-Study” have been amended to only reflect the original protocol design.

The following changes were made to the protocol with the removal of the sub-study:

- Title updated to remove the sub-study – Cover page and Protocol Summary
- The following sections, tables, and figures from Protocol Amendment 1 were deleted and subsequent sections have therefore been renumbered, as applicable: Sections 1.1.5, 1.3, 1.3.1, 1.4.5, 1.4.5.2-1.4.5.4, 2.1, 3.1.2, 4.4-4.4.3, 5.2, 6.8-6.8.5, 7.1.2, 7.2.4-7.2.4.3, 8.4-8.4.2, 9.2.1, 9.3.2, 9.6.7-9.6.7.2, 10.7.2-10.7.2.2, and 11.3. Tables 3, 4, 6, and 8-10. Figures 1 and 3.
- The following sections and figure have been updated to remove all references to the sub-study: Protocol Summary, Sections 3.1-3.3, 4.1, 6.5, 7.2, 7.2.4, 7.4.3, 7.5-7.6, 7.8, 9.1, 9.5, 9.7-9.7.2, [REDACTED] 10.1, 10.2.3, 10.2.5, 10.3, and 10.4.1-10.6. Figure 2.
- References to “Main study” have been removed or revised to “study” throughout.

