1.1. Additional Clarifications and Corrections

Other changes included in this amendment are summarized below. These changes are based on recommendations received from internal discussions and expert opinions.

- Updated language in Section 6.7.1. Symptoms Response Assessment
 - To ensure every possible attempt to collect symptom response information is made, wording has been updated to include alternate modalities.

- Updated language in Section 6.5 Response Assessment
 - Revised language regarding the time point frequency and assessments to be completed. Aligned frequency of all “response assessments” to occur every six (6) cycles after Cycle 24 which includes spleen imaging (in addition to spleen size by palpation and Myelofibrosis Symptom Assessment Form [MFSAF])
- Updated language in Sections 7.4.2 Management of Encephalopathy Including Wernicke’s
 - Updated Section 7.4.3- Management of Encephalopathy including Wernicke’s language to empirically start parenteral thiamine supplementation for subjects with thiamine levels < 30 nM/L
- Updated language in Section 7.4.2 Thiamine Supplementation, Monitoring, and Correction
 - Updated Section 7.4.3 title from “Thiamine Monitoring and Correction” to “Thiamine Supplementation, Monitoring, and Correction” to reflect updated language for required thiamine supplementation
 - Revised language to state that oral thiamine supplementation of 100 mg or equivalent is mandatory for all subjects throughout the treatment period until study medication is discontinued and through the 30-Day Follow-Up visit
 - Revised language to reflect thiamine level monitoring to be taken in a fasting state at the start of Cycles 1, 2, 3 and every third cycle thereafter, including end of treatment (EOT) visits
 - Revised language to include new monitoring parameters and thiamine level thresholds for encephalopathy including Werneck’s Encephalopathy (WE) monitoring
 - Updated guidance to site if subject develops signs or symptoms suggestive of WE, to follow instructions updated in Section 7.4.2
 - For thiamine levels below normal range but > 30 nM/L without signs or symptoms of WE – updated language to increase thiamine supplementation to twice the daily dose (100 mg to 200 mg)
 - Updated guidance to site to contact Medical Monitor regarding low thiamine level
 - For thiamine levels < 30 nM/L without signs or symptoms of WE – updated language to stop oral thiamine supplementation and start intravenous (IV) thiamine at therapeutic dosages

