1. JUSTIFICATION FOR AMENDMENT

As of 12 Feb 2020, approximately 20 subjects have been enrolled into the main study of FEDR-MF-001 of which ~2 have completed at least 8 cycles of treatment with fedratinib.

Other significant changes included in this amendment are summarized below. These changes are based on recommendations received from the [REDACTED] expert opinion, and internal discussions.

- Modifications to the eligibility criteria
 - To ensure subjects are evaluable for the primary and key secondary endpoints in the study, an additional exclusion criterion is added requiring subjects to have a minimum life expectancy of 6 months. Subjects with a white blood cell count $> 100 \times 10^9/L$ are not eligible to participate in the study.
Revised section: Section 4.3;
- Surveillance of suspected encephalopathy, including Wernicke's encephalopathy, in patients receiving or who have received fedratinib from any source [REDACTED]
 - The objective, endpoint, and further reference in the protocol to assess the effectiveness of the risk mitigation strategy for Wernicke encephalopathy is updated to include Encephalopathy, including Wernicke's.
Revised sections: Protocol Summary, Section 1.2.1, Section 1.4.1, Section 1.4.2, Section 4.3, Table 5, Section 6, Section 7.4, Section 9.7.3 and Section 10.7.1;
 - Language is revised to clarify that platelet and red blood cell transfusion history will be collected 84 days prior to enrollment. This will establish the subject's baseline transfusion status information.
Revised sections: Table 5, Section 6.1 and Section 8;
- Lipid testing is included in the study [REDACTED]
 - Lipid profile monitoring is added [REDACTED] [REDACTED] since lipid profile changes have been observed in patients treated with ruxolitinib. This request is to better understand if the lipid profile changes are specific to ruxolitinib or if changes could possibly be a Janus kinase inhibitor class effect.
Revised sections: Table 5, Section 6.1, Section 6.2, Section 6.2.1, and Section 6.4;
- The language is updated throughout the protocol for concomitant administration of fedratinib with clinically relevant cytochrome P450 inducers, inhibitors, substrates, and transporter substrates to align with the information included in the Inrebic® label recently approved by the FDA
 - The eligibility criteria are updated to exclude subjects receiving concomitant treatment with or use of pharmaceutical, herbal agents or food known to be strong

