1.2. Minor Corrections, Clarifications and Administrative Changes

- Added clarification on the trademark and availability of ruxolitinib – Section 1.1.3 and Section 1.4.1;
- Revised JAKARTA adverse event percentages to align with the citation – Section 1.2;
- The Table of Events screening range is clarified to -28 to -1 days. The visit description in the Table of Events for *Risk mitigation for GI & WE* is updated to *Risk mitigation for GI & Encephalopathy including Wernicke's* – Table 5;
- Described the physical exam requirements further to include clinically significant findings – Section 6.1;
- Clarified sections of management of gastrointestinal (GI) AEs and Encephalopathy including Wernicke's is for fedratinib – Section 7.3 and Section 7.4;
- Added language for clinical guidance on the minimum required thiamine dosing for treating subjects with thiamine levels below normal to maintain a consistent treatment approach as was used in the JAKARTA Phase 3 study – Section 7.4.3;
- Included a recent change to the standard protocol template language stating that literature “book” values and normal ranges will be utilized for local laboratory results – Section 9.7;
- Updated details on Study discontinuation and SAE reporting to align with other sections – Section 11.2;
- Added a clarifying note to ensure reference to the author's definition of constitutional symptoms for Dynamic International Prognostic Scoring System (DIPSS) calculation – Appendix F;
- Corrected typo in the Progressive disease criteria and added response categories for stable disease and relapse – Appendix O;
- Other clarifications, corrections of minor typographical errors and incidental formatting changes were made throughout the document;
- References were updated based on updated details throughout the document – Section 17.

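### Thiamine for all subjects came in by amendment after at least about 20 of 110 had enrolled, but the planned thiamine and encephalopathy summaries do not separate time before and after it

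*Combined protocol and SAP*

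**What the plan says.** **Objective and analysis.** Table 1 lists, as a secondary objective, assessing how effective the risk mitigation strategy for encephalopathy is. It refers to one strategy. Section 9.7.3 plans one incidence analysis and a by-visit thiamine analysis: "Analysis of thiamine levels will be at screening, on Day 1 of the first 3 cycles, every third cycle and at the EOT". Section 9.7.4 adds: "Summary of laboratory data (including thiamine levels) and change from baseline will also be performed by subject and by cycle". Section 9.7 applies the safety population throughout. Section 10.7.1 makes any thiamine level below the normal range an adverse event of special interest (AESI), and 9.7.2 summarises AESIs in the same way as other adverse events.

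**Current strategy.** Section 7.4.3: "Start oral thiamine supplementation at a minimum daily dose of 100 mg (or equivalent) at Cycle 1 Day 1". It also requires fasting samples at the scheduled visits. Below 30 nM/L, fedratinib is held and IV thiamine is given.

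**When this came in.** The later amendment's justification records: "The Steering Committee made the recommendation to implement prophylactic thiamine supplementation for all study subjects". Its list of clarifications says that "oral thiamine supplementation of 100 mg or equivalent is mandatory for all subjects throughout the treatment period", and also "Revised language to reflect thiamine level monitoring to be taken in a fasting state at the start of Cycles 1, 2, 3". The earlier amendment's justification states: "As of 12 Feb 2020, approximately 20 subjects have been enrolled into the main study of FEDR-MF-001". The minor corrections of that earlier amendment describe a narrower use of thiamine: "Added language for clinical guidance on the minimum required thiamine dosing for treating subjects with thiamine levels below normal".

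**The concern.** Encephalopathy is expected to be rare, so thiamine levels and low-thiamine AESIs carry most of the information on this objective. Routine supplementation acts directly on both. Three summaries are affected.

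- **Low-thiamine AESI rate.** A pooled rate averages two regimens and estimates neither.
- **Change from baseline.** Baseline is the last value up to the first fedratinib dose, and routine thiamine now starts on that same day. In later enrollees the change reflects fedratinib plus supplementation. In early enrollees, before the switch, it reflects fedratinib plus whatever thiamine was given for low levels.
- **Thiamine by cycle.** Early enrollees passed their early cycles before the change and some reached later cycles after it. The share of pre-change samples therefore falls with cycle. If supplementation raises levels, the pooled mean rises with cycle even when levels are flat under each regimen. A reader could take that as mitigation working, or could miss a fall on fedratinib without routine thiamine.

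The amendment summaries are used here only to show that subjects were treated under both regimens. That they differ from the current text is not the complaint.

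**Working it through.** **Plan's own figure.** There is none for this endpoint: no sample size, threshold or test. The trial's only sizing figure concerns the primary endpoint. It reproduces (exact power 0.915 with 100 evaluable subjects, against about 90% stated) and is not affected.

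**Step 1: what the documents fix.** About 20 subjects were enrolled by 12 Feb 2020 and 110 are planned. 20/110 = 18.2% started before the change. This is a minimum.

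**Step 2: no encephalopathy case.** The exact 95% upper limit for 0 of n is 1 − 0.025^(1/n).
- Pooled, n = 110: 3.3%.
- Subjects supplemented from their first dose, at most 110 − 20 = 90: 4.0%.
- If only 55 were: 6.5%.

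The pooled limit is therefore tighter than the current regimen alone supports.

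**Step 3: drift by cycle.** Let p_k be the share of Cycle k Day 1 samples taken before the change. The pooled mean is p_k × (mean before) + (1 − p_k) × (mean after). With both means constant over cycles, the pooled mean moves from Cycle 2 to Cycle 12 by (p_2 − p_12) × (after − before).

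The documents do not give p_k, so the following are assumptions:
- The change is placed at 12 Nov 2020, 274 days after 12 Feb 2020.
- First enrolment was 238 days before 12 Feb 2020, because about 2 subjects had completed at least 8 cycles (224 days). Enrolment to 20 was linear, 20/238 = 0.084 per day, about 2.6 per month.
- There is no drop-out.

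Subjects past Cycle k Day 1 at the change are those enrolled at least 28(k − 1) days earlier.

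| Enrolment after 12 Feb 2020 | Enrolled at change | p_2 | p_12 | Drift (share of the before/after difference) |
|---|---|---|---|---|
| None until the change | 20 (18.2%) | 20/110 = 18.2% | (20 − 34 × 0.084)/110 = 15.6% | 2.6 points |
| Same pace, 0.084 per day | 20 + 274 × 0.084 = 43 (39%) | (20 + 246 × 0.084)/110 = 37.0% | 15.6% | 21.4 points |

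A later change date would raise the enrolled share.

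**Step 4: low-thiamine AESIs.** Assume 12 months' treatment each (the average expected in Section 3.2), risk proportional to time, and, for illustration only, rates of 10% before and 2% after. Up to the change, the first 20 subjects contribute 11.4 months each on average (uniform from 9 to 16.8 months, capped at 12). Any further enrollees contribute 4.5 months each.
- None further: pre-change share of time = 20 × 11.4/(110 × 12) = 17.3%. Pooled rate = 0.173 × 10% + 0.827 × 2% = 3.4%.
- Same pace: (20 × 11.4 + 23 × 4.5)/1320 = 25.1%. Pooled rate = 0.251 × 10% + 0.749 × 2% = 4.0%.

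Both compare with 2% under the current regimen. If risk is concentrated early in treatment, the pooled rate is higher.

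**The case against.** **The plan is silent; it does not state that it pools.** Section 9.1 calls Section 9 an overview and leaves final methods to a SAP, whose text is not in the documents. Section 9.7.3 says what the assessment will include, which is not exhaustive, and 9.7.2 allows further safety analyses related to prophylaxis. This stands in part: the SAP may already contain a split. But the 9.7.2 provision is conditional and its example is nausea, vomiting and diarrhea. Nothing readable supplies the split for thiamine or encephalopathy.

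**Before the change is not the same as unsupplemented.** This stands. The earlier 7.4.3 text is not visible. The earlier amendment's summary mentions dosing for low levels and when to stop supplementation, so some early subjects took thiamine. Whether early samples were fasting is also unknown. For both reasons the split should follow each subject's own dates and not the protocol version.

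**The consequence is limited.** This also stands. It is a descriptive item in a single-arm study, and the few encephalopathy cases would be dated and identifiable one by one. The thiamine and AESI tables do not have that protection.

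**Stronger readings a reader might infer.**
- That most subjects started under the old regimen. At the planned pace (110 in 18 months, 6.1 per month), 20 + 9 × 6.1 = 75 (68%) would have enrolled by 12 Nov 2020. That needs enrolment to more than double from about 2.6 per month.
- That thiamine changed on 12 Nov 2020. That date belongs to the decision not to run the sub-study. No thiamine implementation date is given.
- That the reported Wernicke's case arose in this trial. It is attributed to the ongoing clinical program.

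**Conclusion.** The concern holds in limited form. At least about 18% of planned subjects started before thiamine for all, and the current analysis sections do not separate their earlier experience. If followed as written, thiamine levels by cycle, change from baseline and low-thiamine AESI rates would not describe the strategy now in the protocol.

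The size of the distortion cannot be fixed from the documents. Under the stated assumptions the Cycle 2 to Cycle 12 drift is between 2.6% and 21.4% of the before/after difference. The lower end is negligible; the mixing of AESI rates remains even there. These figures depend on an assumed change date, an assumed enrolment pace and no drop-out. They also treat all pre-change time as one regimen, which overstates the contrast to the extent that early subjects were already taking thiamine.

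The primary endpoint is not touched. The later amendment lists no change to the management of gastrointestinal events in Section 7.3, so that part of 9.7.3 can stay pooled. This is a cheap improvement to a named secondary objective.

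**What to change.** In the SAP:

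1. Define for each subject the date of first prophylactic thiamine (at least 100 mg daily) from the dated concomitant medication pages required by Section 8. Flag thiamine started in response to a documented low level.
2. Report thiamine levels and change from baseline by cycle, low-thiamine AESIs and any encephalopathy separately for:
   - (i) subjects supplemented from Cycle 1 Day 1;
   - (ii) time before supplementation;
   - (iii) time after the switch in subjects who changed.
3. Use events per patient-month for (ii) and (iii), assigning each event to the period in which it began.
4. Flag samples as fasting or not where this is known.
5. State that (i) and (iii) describe the current strategy and that the pooled figure is supportive.

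If the SAP already does this, only confirmation is needed.

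**Cost.** A paragraph of SAP text and a few more descriptive tables, with no new visits, samples or medication dates. The groups will be small and not randomised, they differ in calendar time, and fasting status may be missing for early samples. The split should therefore be presented as description and not as a test of supplementation.
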